### **10. Recent documented acute kidney injury without documentation of recovery to stable baseline**

## STUDY DURATION: 1 day

## STATISTICAL AND ANALYSIS PLAN

Calculation of clearance Urinary clearances for each period will be calculated using the equation:

$$\text{Urinary Clearance} = U_{i1}V_1/\exp[(\ln P_{i0} + \ln P_{i1})/2]$$

where U and P are defined as urine and plasma concentrations of iothalamate, respectively, V is the urine flow rate, and subscripts 0 and 1 denote the samples obtained at the beginning and end of collection period i. Values will be normalized to body surface area.

Performance metrics Bias will be assessed as the median difference between mGFR and eGFR, and precision as the interquartile range for the differences. Accuracy will be assessed as root mean squared error and as the percentage of estimates that are greater than 30% from mGFR (1- P30). Confidence intervals will be calculated by bootstrap methods (2,000 bootstraps). The significance of the differences among equations will be determined using McNemar test for 1 -P30 and comparing the eGFR estimates for their ability to predict mGFR thresholds of 60, 45, and 30 mL/min/1.73 m^2.

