 All laboratory tests to be done locally, unless otherwise noted. When laboratory tests are obtained on the same day as NEOD001 administration they should be obtained *prior to* administration of study drug. Pregnancy tests for WOCBP as follows: **Screening:** serum test within 28 days before Month 1-Day 1; **Month 1:** serum test within 24 hours before Month 1-Day 1; **Months 2-12:** serum test preinfusion; **EOS/ETD:** serum test; **90 ( $\pm 5$ ) days after the last study drug administration:** serum test.

 Serum free light chain studies, U-PEP, U-IFE, SPEP and S-IFE will be obtained prior to administration of NEOD001 or placebo.

[figure not shown]
 Archive of baseline and confirmatory EOS visit urine samples, in consenting patients, from first morning urination will be maintained at Tufts. Samples should be obtained during the screening period before the renal biopsy. Samples will be shipped same-day overnight in kits provided. These samples will be banked for future unspecified testing.

 Renal biopsy at study entry is standard of care. Renal biopsy should be obtained after mGFR and other urine studies, including archived urine sample, have been performed. A portion of the biopsy is routinely used for frozen section and, in consenting patients, will be cryopreserved in RNA Later for future molecular testing.

 Standard-of-care follow up will include local testing every 3 months of all laboratory studies included in the confirmatory visit during the OLE study.

 Inflammatory biomarkers include IL-6, IL-8, TNF $\alpha$ , C3 and C4, CRP, SAA (A-SAA), and tryptase (at screening only). Biomarkers should be repeated if clinically indicated, i.e. the subject has a hypersensitivity reaction.

 Serum creatinine and 24 hour urine collection, including UPEP, to be sent to central lab (Covance).

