## Appendix 9 Measuring GFR by [name]

### STUDY RATIONALE:

Measured GFR is the gold standard for assessing kidney function. However, measuring GFR is costly and complicated both for routine clinical use and research studies. Currently, kidney function is estimated in routine clinical practice and most research settings using estimating equations based on serum creatinine. Although serum creatinine is inexpensive, convenient, it has several limitations as it varies with age, gender and especially muscle mass and diet. Since muscle mass and diet can change with illness and its recovery, estimated GFR from serum creatinine is not very accurate or sensitive at detecting change in populations with acute or chronic illness. Novel filtration markers such as low molecular weight proteins (serum cystatin C,  $\beta$ -trace protein and  $\beta$ -2-microglobulin) and novel metabolites (accuGFR) are emerging and since they are not based on muscle mass may provide more accurate estimates especially in patients with illness. However, explicit testing is required since these markers might be influenced by inflammation and disease, as well as the treatment itself.

There is great need to accurately measure GFR for both clinical care and research studies involving new treatments. To date, there is no published data on the concordance of measured GFR and estimated GFR in patients with AL amyloidosis. The aim of this study is to assess the performance of CKD-EPI creatinine, to those using novel filtration markers in comparison to iothalamate clearance measured in AL amyloidosis patients.

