**iothal=iothalamate**

 U1 will be collected between 60 and approximately 105 minutes. U2 will be collected between 105 and approximately 150 minutes. Urine samples will be sent to Mayo Clinic, Rochester.

 Prior to aliquot, the volume of the collection will be determined

 Plasma blood samples will be collected within 5 minutes of void.

 Plasma samples to be sent to Mayo Clinic, Rochester.

 Serum samples for assay of creatinine, urea and cystatin and optional stored samples, to be sent to University of Minnesota.

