## INCLUSION AND EXCLUSION CRITERIA for GFR study

### Inclusion Criteria

1. Consenting participants in RAIN

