### Exclusion Criteria

The subject must not meet any of the following:

1. Excluded from RAIN
2. Persons with known allergic reaction to iohexol, iodine, iothalamate or shellfish
3. Inability to cease taking medications that affect creatinine levels (e.g. trimethoprim or trimethoprim-sulfamethoxazole and cimetidine) for two days prior to the study visit
4. Inability to maintain a stable regimen of anti-inflammatory agents and angiotensin converting enzyme inhibitors for one week prior to study visit
5. Current treatment with amiodarone or metformin. Metformin can be stopped the day prior.
6. Acute exacerbation of asthma or chronic obstructive lung disease in the past three months requiring hospitalization or oral steroid therapy
7. Hypercalcemia, defined as a calcium of > 11 g/dL
8. Weight loss >10% over 2 months prior to Day 1 of this study
9. Had a major surgical procedure within 4 weeks prior to mGFR testing

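### Appendix 9 compares eGFR equations at an mGFR threshold of 30 in a sample that had to have eGFR of at least 30 to enter, so that one comparison is probably biased against creatinine and rests on very few patients

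*Combined protocol and SAP*

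**What the plan says.** Appendix 9 (Study Rationale) sets out to "assess the performance of CKD-EPI creatinine, to those using novel filtration markers in comparison to iothalamate clearance" in AL amyloidosis. Its Statistical and Analysis Plan lists bias, precision, root mean squared error and 1-P30, with a McNemar test for 1-P30, and adds "comparing the eGFR estimates for their ability to predict mGFR thresholds of 60, 45, and 30 mL/min/1.73" mL/min/1.73 m². It names no metric for that last comparison.

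The sub-study's inclusion criterion is "Consenting participants in RAIN", and its first exclusion is "Excluded from RAIN". Inclusion criterion 5 in the synopsis is CKD 1 to 3, given as eGFR of at least 30. Section 4.1 gives the CKD stages without a figure. The open-label extension checklist equates CKD 4 or 5 with eGFR below 30. None of these places names the equation behind the entry eGFR.

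On the source of creatinine, a footnote to Table 1 says "All laboratory tests to be done locally, unless otherwise noted", and another sends serum creatinine to the central laboratory. For the GFR day, a footnote to Table 3 in Appendix 9 says "Serum samples for assay of creatinine, urea and cystatin and optional stored samples, to be sent to University of Minnesota". Table 4 marks creatinine both at RAIN screening and on the GFR day. The Statistical and Analysis Plan does not say which is analysed. Section 3.1 makes the clearance study optional.

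**The concern.** The comparison asks which equation best identifies patients with mGFR below 30. The entry rule removes candidates whose eGFR was already below 30. If that eGFR came from creatinine, the patients removed are those creatinine placed below the threshold. Most patients with mGFR below 30 who remain are there because creatinine read high. The novel-marker estimates have not been filtered in this way, so two equally accurate equations would not look equal at 30. Appendix 9 neither mentions this nor allows for it.

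Appendix 9 says there are no published data on agreement between measured and estimated GFR in AL amyloidosis. A misleading result at 30, the boundary of CKD stage 4, would therefore have little to be checked against.

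**Working it through.** Appendix 9 gives no sample size, power or expected number below 30, so there is no figure of the plan's own to reproduce.

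**Inputs from the documents.** Thresholds 60, 45 and 30 (Appendix 9); entry at eGFR of at least 30 (synopsis); RAIN participants only (Appendix 9); about 100 randomised, which is the ceiling for an optional sub-study (sections 3.1 and 3.3).

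**Assumptions, not in the documents.** The entry eGFR is creatinine-based. Candidate mGFR is lognormal, with median 50 to 60 (log-SD 0.45) or 55 to 70 (log-SD 0.5), and is treated as exact. Each equation has a persistent within-person error of log-SD s = 0.15 to 0.25 and draw-to-draw variation c = 0.05. Both equations are equally accurate, and their errors are independent unless stated.

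**One patient by hand.** Take mGFR 27, s = 0.20, c = 0.05.
- Total log-SD: √(0.20² + 0.05²) = 0.206.
- Chance that either equation reads below 30 without selection: Φ(ln(30/27)/0.206) = Φ(0.511) = 0.695.
- The screening and GFR-day creatinine estimates share the persistent error. Their correlation is 0.20²/(0.20² + 0.05²) = 0.941, and the chance that both read below 30 is 0.647.
- Chance that the GFR-day creatinine reads below 30, given that screening was at least 30: (0.695 − 0.647)/(1 − 0.695) = about 0.16.
- The novel marker, with independent error, stays at 0.695.

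**Whole sample, by simulation (2 million candidates per scenario).**

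| Quantity | Creatinine, GFR day | Equally accurate novel marker |
|---|---|---|
| Sensitivity for mGFR < 30, no selection | 0.73–0.83 | 0.73–0.83 |
| Same, entry eGFR ≥ 30 | about 0.11–0.21 | about 0.64–0.67 |
| Same, error correlation 0.5 | 0.12–0.21 | 0.45–0.50 |
| Sensitivity for mGFR < 45, entry eGFR ≥ 30 | 0.68–0.81 | 0.73–0.82 |
| Median mGFR − eGFR, entry eGFR ≥ 30 | −0.3 to −1.8 | about 0 |

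Repeat runs agree to within about 0.01 on the sensitivities. If draw-to-draw variation were as high as 12%, creatinine sensitivity at 30 would rise to at most about 0.42. The AUC gap at 30 is about 0.01 to 0.04 with independent errors and about 0.004 to 0.02 with correlation 0.5. At 60 the two sensitivities differ by about 0.01. 1-P30 differs by at most about 0.006.

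**Number of patients.** The share of entrants with mGFR below 30 is 0.9 to 3.8%, or about 1 to 4 people if all 100 took part.

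**Restricting to a higher range (independent errors).** Taking only patients with screening eGFR of at least 45 moves median creatinine bias to about −1.1 to −5.1 mL/min and cuts creatinine sensitivity at 45 to about 0.12–0.22, against 0.67–0.70 for the novel marker. Taking only entrants with mGFR of at least 45 leaves median bias between 0 and −0.2 for both equations.

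**The case against.** A reader might infer that creatinine must fail at 30, with sensitivity of exactly 0. That follows only if the screening eGFR itself is reused and dichotomised at 30. Appendix 9 describes a fresh sample on the GFR day, assayed at a different laboratory, so values below 30 can occur. The objection stands against the 0% figure but does not remove the bias. Both samples fall in the same 28-day screening window and share the person-specific error of the equation.

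The metric is also unstated. The reference list contains a paper on comparing correlated ROC areas. The text does not cite it, but AUC would be a natural choice, and it would shrink the artefact to a few hundredths. That stands too, although an AUC resting on 1 to 4 patients below the threshold says almost nothing.

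The entry equation is not named, so truncation on creatinine is an inference. It rests on Table 1 listing eGFR with serum creatinine and on Appendix 9 saying that creatinine equations are usual in practice and in most research.

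A reader might also fear for the trial's renal endpoints. The documents do not support that. Sections 8.3.1 and 8.3.2 compare eGFR and creatinine outcomes between randomised arms, and none of those analyses uses the equation comparison at 30.

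**Conclusion.** The comparison at 30 is range-restricted by the entry rule, and Appendix 9 does not address this. With a cut-off metric and a creatinine-based entry eGFR it is biased against creatinine, by roughly 0.45 to 0.55 in sensitivity if errors are independent and about 0.3 if they are moderately correlated. With AUC the bias is small. On either metric the sample holds too few patients below 30 to support a between-equation claim. The direction depends on the entry eGFR being creatinine-based, and the sizes depend on the assumed GFR distribution and error sizes.

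The problem is essentially confined to 30. At 45 the artefact is at most about 0.06 in sensitivity, at 60 about 0.01, and the overall metrics barely move. This is a wording matter in a sub-study and leaves the primary and secondary renal endpoint analyses untouched.

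**What to change.** In the Statistical and Analysis Plan of Appendix 9:

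1. Drop 30 from the thresholds at which equations are compared, keeping 60 and 45, or report it as descriptive only. Give the RAIN entry limit as the reason.
2. State that the comparison uses the GFR-day creatinine, and name the metric for predicting thresholds.
3. If a sensitivity analysis away from the entry floor is wanted, restrict it on the reference, for example mGFR of at least 45. Do not restrict on screening eGFR of at least 45. That looks like a natural remedy, but it truncates on the creatinine test a second time, at a threshold still being analysed, and enlarges the bias.

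The cost is a few sentences and, if wanted, one table. The sub-study gives up a between-equation claim at 30, which this sample cannot support.

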## POTENTIAL RISKS AND DISCOMFORTS

Adverse reactions associated with iothalamate include:

### Very Common (10% or higher)

- Hot flashes
- Pain
- Feeling of body warmth

### Common (1-10%):

- Nausea and vomiting
- Hives
- Inflammation of your nose

### Uncommon (0.1-1%)

- Facial flush
- Rash
- Cough

### Rare (0.01-0.1%)

- Diarrhea
- Dry mouth
- Injection side reaction
- A reaction that resembles anaphylaxis, e.g., by hives, laryngeal edema, or shock, but does not involve IgE antibodies or allergens and therefore it has no allergic basis

### Very Rare (less than 0.01%)

- Renal failure- kidneys stop working normally

Serious events may include severe cardiovascular responses include rare cases of hypotensive shock (not enough blood and oxygen flow to the body's major organs, including the brain, which can cause dizziness, blurry vision, confusion, weakness, fatigue, and nausea), coronary insufficiency (insufficient blood flow through one or more coronary arteries), cardiac arrhythmia or fibrillation (irregular heartbeat), and cardiac arrest (heart attack).

### *Intravenous (IV) Risk*

An IV (a hollow needle/plastic tube) will be placed in participants arm to give the study drug. When the needle goes into a vein, it may hurt for a short time. Also, there may be minor discomfort of having the needle/plastic tube taped to the arm. In about 1 in 10 cases, a small amount of bleeding under the skin will produce a bruise. The risk of a blood clot forming in the vein is about 1 in 100. The risk of infection or significant blood loss is about 1 in 1,000.

### *Risk of Loss of Confidentiality*

When participating in research studies, like this one, there is always a risk that records, samples, or personal / medical information will not be kept completely private. The research team is aware that any loss of confidentiality could have a negative impact on the participant. Each member of the study team will try to maintain the highest level of confidentiality possible in recording, storing, and transmitting information about the participants.

## BENEFITS

Participants may not personally benefit from this sub-study but this testing may help patients in the future.

**Table 4 Schedule of Procedures for mGFR**

Study Procedures	Screening a to be done as part of RAIN screening	Day 1 GFR measured
Informed Consent	X	
Inclusion/Exclusion Criteria	X	
Medical History	X	
Physical Examination	X	
Concomitant Medications	X	
Review Study restrictions/prohibited medications/assess for AKI	X	X
Vital Signs, Height, and Weight		X
ECOG Performance Status	X	
Creatinine to estimate the GFR	X	X
Other filtration marker and stored serum		X
Urine Pregnancy Test b		X
Urinalysis	X	
Measured GFR using urinary clearance of iothalamate		X

bFemales of child-bearing potential only.

## Appendix 10 Renal Gene Expression Profiling

The following abstract describes the systems biology approach of the NEPTUNE project. The RAIN study is NOT using all of the research elements that are used in the NEPTUNE project.

Gadegbeku CA1, Gipson DS, Holzman LB, Ojo AO, Song PX, Barisoni L, Sampson MG, Kopp JB, Lemley KV, Nelson PJ, Lienczewski CC, Adler SG, Appel GB, Catran DC, Choi MJ, Contreras G, Dell KM, Fervenza FC, Gibson KL, Greenbaum LA, Hernandez JD, Hewitt SM, Hingorani SR, Hladunewich M, Hogan MC, Hogan SL, Kaskel FJ, Lieske JC, Meyers KE, Nachman PH, Nast CC, Neu AM, Reich HN, Sedor JR, Sethna CB, Trachtman H, Tuttle KR, Zhdanova O, Zilleruelo GE, Kretzler M.

Design of the Nephrotic Syndrome Study Network (NEPTUNE) to evaluate primary glomerular nephropathy by a multidisciplinary approach.

Kidney Int. 2013 Apr;83(4):749-56. doi: 10.1038/ki.2012.428. Epub 2013 Jan 16.

### Abstract

The Nephrotic Syndrome Study Network (NEPTUNE) is a North American multicenter collaborative consortium established to develop a translational research infrastructure for nephrotic syndrome. This includes a longitudinal observational cohort study, a pilot and ancillary study program, a training program, and a patient contact registry. NEPTUNE will enroll 450 adults and children with minimal change disease, focal segmental glomerulosclerosis, and membranous nephropathy for detailed clinical, histopathological, and molecular phenotyping at the time of clinically indicated renal biopsy. Initial visits will include an extensive clinical history, physical examination, collection of urine, blood and renal tissue samples, and assessments of quality of life and patient-reported outcomes. Follow-up history, physical measures, urine and blood samples, and questionnaires will be obtained every 4 months in the first year and biannually, thereafter. Molecular profiles and gene expression data will be linked to phenotypic, genetic, and digitalized histological data for comprehensive analyses using systems biology approaches. Analytical strategies were designed to transform descriptive information to mechanistic disease classification for nephrotic syndrome and to identify clinical, histological, and genomic disease predictors. Thus, understanding the complexity of the disease pathogenesis will guide further investigation for targeted therapeutic strategies.

### RAIN study: renal biopsy specimens

Patients on RAIN will be given the opportunity to consent to having a portion of their renal biopsy tissue used for gene expression analysis. Gene expression analysis involves extracting RNA from the cryopreserved tissue, making complementary DNA from RNA, and analyzing the level of expression by use of The GeneChip™ Human Genome U133 Plus 2.0 Assay (Affymetrix, Santa Clara, CA, soon to be a ThermoFisher company). The data that is generated will be analyzed by the computational biologists of the NEPTUNE project in collaboration with biostatisticians from the collaborators (Tufts and ARC; personnel to be identified). The renal biopsy samples (a minimum of 1mm^3) obtained for transcriptional profiling from consenting patients on RAIN will be placed in cryovials with RNA Later and stored at -80° C in the RAIN centers. The procedures used are identical to the NEPTUNE standard operating procedures which [name] has shared with the medical monitor ([name]) and the sponsor (Tufts).

### ARC, RAIN and NEPTUNE

The ARC is seeking grant support for the ancillary studies of RAIN, including the transcriptional profiling of renal biopsy specimens. The investigators at the University of Michigan, led by [name], will receive the specimens for transcriptional profiling from the RAIN centers when funding is secured. Philanthropic support will also be provided for the studies by the ARC; in the event that funding for the transcriptional profiling is not

forthcoming, renal biopsy specimens will be sent to and stored at Tufts in LN2 storage in [name] s laboratory.

## Appendix 11 Open Label Extension Study

The purpose of the study is to evaluate the long-term safety and effects of NEOD001 in subjects with AL amyloidosis who were previously enrolled and treated for at least 12 months in the main study. In the absence of unacceptable treatment-related toxicity or withdrawal of consent, subjects may receive NEOD001 at the discretion of the Investigator for up to 12 infusions.

### Estimated Study and Treatment Duration

A subject may receive up to 12 infusions of NEOD001 at the discretion of the Investigator. A subject's study duration may be up to 13 months, consisting of a Screening and Treatment Phase (12 months), and the End of Treatment (EOT) Visit 30 ( $\pm 5$ ) days after the last dose.

### Definition of End of Study

The study will end when the last subject completes 12 months of study treatment and the EOT Visit.

**Table 5: OLE Table of Assessments**

		Treatment		EOS Visit
		Screening/ Month 1 Day 1	Months 2 through 12 Day 1 ( $\pm 5$ days)	
	Informed Consent			
	Eligibility Review			
	Prior/Concomitant Medications	X	X	X
	Adverse Event Assessment		X	X
	Physical Exam	X	X	X
	Vital Signs	X	X	X
	ECOG PS/ NYHA Class	X	X	X
Laboratory	Hematology & Chemistry (including serum creatinine, eGFR and amylase) 	X	X	X 
	Coagulation	X	X	X
	Troponin T or I	X		X
	NT-proBNP	X	X (Months 3, 6, 9, 12)	X
	BNP	X	X (Months 3, 6, 9, 12)	X
	Pregnancy (WOCBP  )	X	X	X
	Serum Free Light Chains	X	X (Months 3, 6, 9, 12)	X
	Serum & Urine PEP 	X	X (Months 3, 6, 9, 12)	X

Serum & Urine IFE	X	X (Months 3, 6, 9, 12)	X
Urinalysis -Dipstick	X	X (Months 3, 6, 9, 12)	X
24-hr Urine Protein Collection for total volume, total protein, creatinine clearance, protein/creatinine ratio, and albumin) 	X	X (Months 6) 	X 
NEOD001 infusion	X	X	
RNB: SF-36	X	X (Months 3, 6, 9, 12)	X

 Serum creatinine to be sent to central lab (Covance) at EOS visit for subjects who have maintained an hematologic response from baseline.

 24 hour urine, including UPEP, to be sent to central lab (Covance) at month 6 and at EOS visit.

## OLE Checklist for Eligibility

### Inclusion:

Subjects must meet **all** of the following criteria:

1. 18 years of age or older
2. Completed entire active study period (12 months) on RAIN with no unacceptable treatment-related toxicity.
3. CKD 1, 2 or 3
4. ECOG Performance Status  $\leq$  2
5. Clinical laboratory values:
  - o Absolute neutrophil count  $> 1000/\mu\text{L}$
  - o Platelet count  $> 75,000/\mu\text{L}$
  - o Total bilirubin  $\leq 1.5 \times \text{ULN}$
  - o Alkaline phosphatase  $\leq 5 \times \text{ULN}$
  - o ALT or AST  $\leq 3 \times \text{ULN}$
6. Voluntary written consent must be given before performance of any study-related procedure not part of standard medical care with the understanding that consent may be withdrawn by the patient at any time without prejudice to future medical care.

